4 STUDY DESIGN

4.1 OVERALL DESIGN

Hospital Discharge Study

This is a prospective, randomized, controlled, pragmatic trial of a pharmacist-led intervention aimed at reducing readmissions. The study will focus on discharge utilization among patients most at risk for post-discharge ADEs: recently discharged older adults taking ≥ 10 medications or ≥ 3 high-risk medications.

Focus Groups and Interviews

This is a qualitative study employing interviews, observations, and focus groups aimed at understanding implementation barriers and facilitators. Drs. [name] and [name] and study staff will conduct 3-day site visits to hold focus groups regarding intervention expectations, how the intervention is being implemented, barriers/facilitators to adoption and implementation, and adaptations made during delivery.

Towards the end of the trial, [name] and study staff will use phone interviews to determine any changes to the implementation of PHARM-DC that occurred during the RCT, as well as to understand whether and how institutions will address the maintenance of PHARM-DC after the study ends.

We will use qualitative methods to the reach of the intervention (overview in **Table 6** above), and to investigate several hypotheses developed using RE-AIM as a guide.

We hypothesize that *staff adoption* will be facilitated by:

(1) units and sites with better safety culture and teamwork and

(2) unit-based (vs central) pharmacists, whereas barriers to *staff adoption* will include:

- (1) difficulties associated with coordinating a time for discharge counseling (patients are frequently anxious to leave as soon as discharge orders are placed, but the discharge medication regimen is not usually available before this time), and
- (2) that even when problems are identified, lack of resources may still be an issue (e.g., medications with expensive copayments). We hypothesize that *implementation consistency* will be higher and that *adaptations* will be lower when pharmacists are not overwhelmed by other responsibilities, and on medical (vs surgical) units.

Surveys to Assess Organizational Context: We will assess safety culture with the AHRQ Patient Safety Survey. Individuals who participate in the focus groups/interviews will be asked to complete the survey prior to participating in the study.

The observations will take place at the two study sites (CSMC and BWH). They may include observations of patients/caregiver interactions. Researchers will not collect any PHI. Observations will include the collection of information such as:

- Amount of time spent by pharmacists on each individual task
- Challenges pharmacists have when attempting to contact caregivers, nurses, pharmacist technicians, primary care physicians, and attending physicians
- Number of sources that pharmacists use (SureScripts, retail pharmacies, asking caregivers) to put together medication reconciliation information
- Challenges pharmacists have when trying to contact patients (e.g. patient doesn't answer the phone)
- How pharmacists divide up work when there are a lot of patients in the study (e.g. how they each have a floor to cover and how they cover for each other when one is busy or is out).

Time and Motion Study

This is a time-and-motion study aimed at understanding how much time during the day pharmacists spend on activities related to the hospital discharge (and post-discharge) interventions. During the trial, we will use time-and-motion methodology to understand how much pharmacist time is needed for PHARM-DC. Coupled with data on post-discharge utilization, this will enable us to conduct economic analyses.

Researchers will collect pharmacist demographics, including:

1. Name
2. Study site
3. Years of experience as a pharmacist
4. Years of experience in TOC
5. Years of Experience in Hospital-Based Pharmacy
6. Years of Residency Training
7. Month and year that you started working at the study site
8. Month and year that you started delivering the PHARM-DC intervention
9. Type of Residency Training
10. List of Board Certifications and Credentials

5 STUDY POPULATION

5.1 INCLUSION CRITERIA

Inclusion criteria include:

- Being discharged from a medical ward, **AND**
- ≥ 55 years old **AND**
- ≥ 10 chronic prescription medications

OR

- ≥ 3 high-risk medications (anticoagulants, antiplatelets, insulin, oral hypoglycemics, and) before or during hospitalization

5.2 EXCLUSION CRITERIA

Exclusion criteria include the following:

- Expected discharge to another state, acute care facility, psychiatric facility, or locked facility (including locked skilled nursing facility, jail, or prison) **OR**
- Expected leaving hospital against medical advice (AMA) or actual AMA **OR**
- Homeless **OR**
- On hospice **OR**
- Already enrolled into study during prior discharge in previous year **OR**
- Expected to receive pharmacist-led post-discharge medication management regardless of the trial **OR**
- Patients admitted by admitting or attending Primary Medical Doctors who have a specialty that is not Internal Medicine or Family Medicine **OR**
- Expected post-discharge setting not conducive to the studied medication management intervention **OR**
- Patients admitted with a suspected or confirmed diagnosis of COVID-19.

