Description of Sites/Facilities Enrolling Participants: Two sites will participate in this study: an academic medical center (Brigham and Women's Hospital in Boston, Massachusetts) and a university-affiliated community hospital (Cedars-Sinai Medical Center in Los Angeles, California ¹) that has some community physicians.

Description of Study Intervention: *Pharmacist-led Hospital Discharge Care Intervention:*
Eligible pharmacists (those with training in transitions of care) at the two sites will receive a list of patients currently admitted to the hospital who meet the inclusion/exclusion criteria. Eligible patients will meet with a clinical pharmacist for medication reconciliation.

Clinical pharmacists will conduct an initial medication regimen assessment, which will use tools in the PHARM-DC Toolkit to identify potentially inappropriate medications. Patients and/or their caregivers will undergo a pre-discharge intervention, where clinical pharmacists will anticipated discharge medication changes.

The Toolkit content and 1-2 hours of introductory training add three major components:

1. Pharmacists will use the *PHARM-DC Toolkit*, which *summarizes the evidence* for post-discharge medication management. The Toolkit includes a (1) the Start Actions for Assessing Adherence Barriers worksheet, integrated into an Epic template, (2) the Beers Medication List, (3) Pre-Discharge Worksheet, integrated into an Epic template, (4) Up-to-Date

Section on prescribing to older adults, (5) Discharge Worksheet, integrated into an Epic template, (6) Post-Discharge Worksheet, integrated into an Epic template.

2. Pharmacists will assess patient needs and customize accordingly. All patients will receive one discharge counseling visit and one post-discharge phone call, but pharmacists will find that some patients need further phone calls, interventions, referrals, or other interactions.

During training, trainers will emphasize to pharmacists participating in this study additional, clinically-indicated services may be provided to control group patients to ensure that it is clear that routine services that are part of the PHARM-DC and that the toolkit should not be withheld from the control group if they are clinically indicated.

Study Duration: 36 months

Participant Duration: Participation during one hospital admission/discharge

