1.3 SCHEDULE OF ACTIVITIES (SOA)

(1) *Pharmacist-led Hospital Discharge Care Intervention:*

- a. Eligible pharmacists at each study site will be selected to participate in the intervention based on their training in transitions of care.
- b. Using a daily Epic report generated by EIS, a coordinator at each site will identify eligible patients and notify pharmacists. Trial enrollment will occur for eligible patients admitted every day prior from Monday to Friday.
- c. Randomization will be performed via the REDCap (Research Electronic Data Capture) system.
- d. All eligible patients (both arms) will receive the Best Possible Medication History (BPMH)
- e. Patients in the Study arm:
 - i. On hospital day 1, or as soon as possible: Receive an Initial Medication Regimen Assessment. Clinical pharmacists assess regimen appropriateness, assess barriers to medication adherence, start filling out the Actions for Assessing Adherence Barriers worksheet
 - ii. On hospital day 1, or as soon as possible: Receive a Pre-Discharge Intervention, which, depending on the patient condition, might include a: trial to discontinue certain medications during the hospital; discussion of side effects, flags for new medications prescribed, education about critical barriers to adherence.
 - iii. On day of discharge: Receive an At-Discharge Intervention, which may include a brief discussion of medication changes, discussion of side effects, discussion of red flags for new medications. Clinical pharmacists will also consult with inpatient clinicians and pharmacists to discuss the medication list and will ensure that the e-prescribing is done appropriately.
 - iv. 1-3 days after discharge: Receive a Post-Discharge Intervention, which includes a call with a patient to discuss the patient's regimen, discussion of side effects, red flags of new medications, a motivational interview, a discussion of barriers to adherence. Other tasks might include a phone call with the patient's primary care physician.
 - v. After initial phone call: Some patients, depending on need, might receive a second phone call if needed, a video visit, clinic visit with pharmacist, embedded mental health.
 - vi. For any of the above-mentioned activities, patients may be contacted by pharmacists over the phone instead of in-person to reduce COVID-19 exposure to patients, caregivers, and pharmacists.
- f. Patients in the Control arm:

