5.3 STRATEGIES FOR RECRUITMENT AND RETENTION

Hospital Discharge Study

Eligible pharmacists will be selected by the pharmacy managers at each site. Eligibility includes training in transitions of care and/or post-discharge care.

A daily Epic report will be generated at each site to identify eligible patients. A research assistant will conduct a brief chart review to confirm eligibility before randomizing the patient using REDCap. For quality assurance, operational reports will be obtained from the emergency department and cross-checked with the EIS report to ensure all patients who may be eligible for the study are accurately identified. The study coordinator will stop randomizing patients if the number of patients concurrently receiving the intervention on any given weekday exceeds the workload capacity of pharmacists at each site. Study coordinators will communicate with pharmacists to regularly re-assess the maximum threshold of concurrent patients in the intervention arm. This strategy aims to reduce the potential for pharmacist burnout and to optimize intervention quality.

Once the patient has been randomized to the intervention or control arm, the clinical pharmacist will approach the patients in the intervention arm.

Focus Group/Interviews Study

We will use a purposive sampling design by role and department to determine eligibility. Eligible participants will receive an email from study staff inviting them to participate in the focus groups, and/or interviews. To enhance recruitment, we will offer a \$125 honorarium to nurses and a \$250 honorarium to physicians for their participation in a 60-90 minute focus group or interview.

Time and Motion Study

Pharmacists will be approached for oral consent at the beginning of a clinic day or clinical shift. Potential participants will be approached, given an information sheet, and the nature of the study will be explained. Inclusion Criteria: Pharmacists participating in the PHARM-DC intervention actively seeing patients and responsible for generating the majority of documentation for the clinical visit.

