6.2 MEASURES TO MINIMIZE BIAS: RANDOMIZATION AND BLINDING

Randomization will be performed via the REDCap (Research Electronic Data Capture) system. REDCap is a secure, web-based application supporting data capture for research studies, providing:

- 1) an intuitive interface for validated data entry;
- 2) audit trails for tracking data manipulation and export procedures;
- 3) automated export procedures for seamless data downloads to common statistical packages; and;
- 4) procedures for importing data from external sources.

REDCap will incorporate allocation tables generated in R. Study participants will be randomized 1:1 to the two arms of the study and stratified by site. Arm assignment will not be actively masked, but most clinical personnel and patients will remain unaware of the trial, just as they are unaware of the details of most post-discharge medication management practices currently.

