8.2 SAMPLE SIZE DETERMINATION

We will use a two-sided likelihood ratio test to compare the proportion of patients with utilization within 30 days of discharge between the intervention and usual care groups. Assuming 80% power and a type I error rate of 0.05, a two-sided Z test between two proportions with **4,888 subjects per group** would detect a difference of at least 2.49% from a baseline of 27.5%. Thus, our primary statistical analysis will be a two-sided Z test. We will also compare the baseline characteristics of those subjects across both arms to ensure there are no major differences. All enrolled patients will be analyzed.

Table 5 shows that varying the baseline utilization proportion does not substantially alter the minimum detectable difference. We also performed a sensitivity analysis assuming that 7.5% of patients in the intervention arm were unreachable or refused a phone call. Even at this rate, which is our best estimate from our pilot data, we would have 80% power to detect a difference of 2.54%. Finally, these rates were robust to contamination rates of 2% among patients in the usual care arm. We believe this low rate is a reasonable estimate for contamination, because patients thought to have a clear need for these services will be excluded from the RCT, and because we believe that non-pharmacist clinicians will remain so busy that they will not begin to provide such services to other patients.

Table 5. How Baseline Utilization Affects Minimum Detectable Difference

Percentage of Patients with Utilization within 30 Days of Hospital Discharge		
Usual Care	Intervention	Minimum detectable difference
30.0%	27.44%	2.56%
27.5%	25.01%	2.49%
25.0%	22.59%	2.41%

For the qualitative study, the study will enroll up to 48 people in the focus groups, 15 people in the Year 2 interviews, and 50 people in the interviews per site.

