8.3 POPULATIONS FOR ANALYSES

We will conduct the following analyses:

- Intention-to-Treat (ITT) Analysis Dataset (i.e., all randomized participants)
- Modified Intention-to-Treat Analysis Dataset (e.g., participants who had the in-hospital intervention but did not respond to post-discharge phone calls)
- Per-Protocol Analysis Dataset: defines a subset of the participants in the full analysis (ITT) set who complied with the protocol sufficiently to ensure that these data would be likely to represent the effects of study intervention according to the underlying scientific model (e.g. participants who had both the in-hospital intervention and the post-discharge phone call).

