2. Minimal Risk: The risks to the patients are minimal. After the medication history is taken for patients, the patients are randomized into either the treatment or control group. However, if a clinician believes that the patient would benefit from the pharmacist consult and/or post-discharge phone call, the patient will meet with the pharmacist regardless of whether they are in the study. Thus, any patient who needs the pharmacist services will receive the appropriate care. The pharmacist participating in the intervention will provide a consult to the physician about medications that should be changed, but the physician will have the final say about any medication changes. This is equivalent to the physician consulting an online resource or receiving a computerized alert about medication recommendations (clinical decision support). Participating in the study will not adversely affect the rights or welfare of the participants since patients who request a meeting with a clinical pharmacist or situations where the attending physician believes the patient should meet with the clinical pharmacist will have every right to do so.
3. Reducing Risk: Since this study is a very low risk intervention, we believe that adding a signed consent form would actually introduce more risk because it would now introduce a document that could identify the participants. We are planning on analyzing the study data at the completion of the intervention and the data will be extracted and only accessed by select study staff. Incorporating documents with PHI may increase the risk for patients of loss of confidentiality.
4. Decrease of Data Validity and Quality: Patients who are randomized to the control group may be more likely not to participate in the study (a phenomenon known as “resentful demoralization”) so there may be systematic bias introduced if patients are asked to consent, which could decrease the validity of study results [see Rebers S, Aaronson NK, Van Leeuwen FE, Schmidt MK. Exceptions to the rule of informed consent for research with an intervention. *BMC medical ethics*. 2016 Dec;17(1):9.].

The risk to subjects is no more than minimal risk to privacy. We have put several measures in place to protect the privacy of subjects and confidentiality of the data:

[1] Personally identifying information will only be available to study personnel.

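### Section 5.2 excludes actual departure against medical advice without tying it to the time of randomization; applied to a randomized patient, the rule conflicts with the ITT set

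*Combined protocol and SAP*

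**What the plan says.** All references are to the combined protocol and SAP.

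- **Eligibility.** Section 5.2 excludes "Expected leaving hospital against medical advice (AMA) or actual AMA". The other criteria in that list about the discharge destination or post-discharge care are limited to what is expected. Only the AMA line adds the event itself.
- **Order of events.** The synopsis (1.1) has pharmacists receive "a list of patients currently admitted to the hospital who meet the inclusion/exclusion criteria". Section 5.3 says "A research assistant will conduct a brief chart review to confirm eligibility before randomizing the patient using REDCap". Section 9.1.1 says "After the medication history is taken for patients, the patients are randomized into either the treatment or control group". For the study arm, section 1.3 says "On hospital day 1, or as soon as possible: Receive an Initial Medication Regimen Assessment".
- **Analysis sets.** Section 8.3 lists "Intention-to-Treat (ITT) Analysis Dataset (i.e., all randomized participants") with no exception. Sections 8.2 and 8.4.1 both say "All enrolled patients will be analyzed".
- **Masking.** Section 6.2 says "Arm assignment will not be actively masked", and adds in the same sentence that most clinicians and patients will not know of the trial.
- **Silence.** No section says what happens to a randomized patient who then leaves AMA. Section 7.1 counts as lost to follow-up only those who leave the state or country or do not answer calls. The examples for the modified ITT and per-protocol sets in 8.3 do not mention AMA.

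**The concern.** A patient who is randomized and then leaves AMA meets an exclusion criterion under 5.2 and belongs to the ITT set under 8.3. Whoever builds the analysis file has to choose between the two, and the plan does not say which prevails. Covariates are extracted from the health record after the intervention ends (section 1.3), so that choice could be made after assignments, and perhaps outcomes, are known.

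At stake is the protection that randomization gives the primary comparison. Study-arm patients have pharmacist contact in hospital and on the day of discharge; control patients receive usual care. The share leaving AMA could therefore differ by arm. If those who leave also differ from other patients in 30-day utilization, removing them creates a difference between arms that the intervention did not cause. The target effect is only about 2.5 points, so even a small artefact counts.

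**Working it through.** **1. Timing.** The sequence in the documents is: admission, listing as a current inpatient, medication history, chart review, randomization, study-arm work from hospital day 1 or as soon as possible, discharge. The relative order of history and chart review is not stated, but both precede randomization. AMA departure can fall in two windows:

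- *Before randomization.* The patient can be screened out under 5.2. No randomized patient is lost and there is no conflict.
- *After randomization.* For anyone randomized this is the only possible window. Section 5.2 read literally excludes the patient; sections 8.2, 8.3 and 8.4.1 keep the patient.

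The criterion as worded covers both windows.

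**2. The plan's own sample size.** Inputs from section 8.2: 27.5% against 25.01%, two-sided alpha 0.05, 80% power. With p̄ = (0.275 + 0.2501)/2 = 0.26255,

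n = [1.96·√(2·p̄·(1−p̄)) + 0.8416·√(p₁(1−p₁) + p₂(1−p₂))]² / (p₁−p₂)²

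= [1.96·√0.3872 + 0.8416·√0.3869]² / 0.0249² ≈ 4,901 per group.

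The plan states 4,888, a 0.3% difference. Power at 4,888 is 79.9% and the detectable difference is 2.49 points, so the stated figure reproduces.

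**3. Loss of precision.** The removed shares are assumptions.

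| Removed from both arms | n per group | Power at 2.49 points | Detectable difference (points) |
|---|---|---|---|
| 0% | 4,888 | 79.9% | 2.49 |
| 1% | 4,839 | 79.5% | 2.51 |
| 2% | 4,790 | 79.1% | 2.52 |
| 3% | 4,741 | 78.7% | 2.53 |
| 5% | 4,644 | 77.9% | 2.56 |

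The cost is about 0.4 to 2.0 power points, which is minor.

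**4. Bias under no true effect.** Let overall utilization be 27.5% in both arms, f the share of an arm removed, and r the utilization among those removed. The remaining rate in that arm is (0.275 − f·r)/(1 − f). Both f and r are assumptions.

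- r = 40%: f = 1% gives 0.2710/0.99 = 27.37%; f = 2% gives 0.2670/0.98 = 27.24%; f = 3% gives 0.2630/0.97 = 27.11%.
- r = 50%: f = 1% gives 0.2700/0.99 = 27.27%; f = 2% gives 0.2650/0.98 = 27.04%; f = 3% gives 0.2600/0.97 = 26.80%.

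| Removed, one arm vs the other | r | Spurious difference (points) | Type I error |
|---|---|---|---|
| equal shares, equal r | any | 0 | 5.0% |
| 1% vs 2% | 40% | 0.13 | 5.2% |
| 1% vs 2% | 50% | 0.23 | 5.8% |
| 1% vs 3% | 40% | 0.26 | 5.9% |
| 1% vs 3% | 50% | 0.47 | 8.1% |

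For scale, the standard error of the difference at 4,888 per arm is √(2·0.275·0.725/4,888) = 0.90 points, so the shifts run from 0.13/0.90 = 0.14 to 0.47/0.90 = 0.52 standard errors. Against the 2.49-point target they are 0.13/2.49 = 5% to 0.47/2.49 = 19%.

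**5. Direction.** When r exceeds 27.5%, the arm that loses more patients looks better. More removals from the intervention arm would favour the intervention; more removals from control would work against it. If r equals 27.5% in both arms, there is no bias whatever the shares.

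**The case against.** The strongest reply is that the sections can be read together: 5.2 is an eligibility list, 5.3 puts the eligibility check before randomization, and the analysis sets are governed by 8.2, 8.3 and 8.4.1. On that reading, patients are screened on 5.2 and everyone randomized is then analyzed. No section orders a randomized patient withdrawn or removed for leaving AMA. A reader might infer from 5.2 that the trial drops such patients, or that actual AMA departure can never be known before randomization. The documents support neither. Enrollment draws on patients already admitted, so some may leave AMA before chart review, and excluding them is ordinary screening.

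It is also fair to say that lack of active masking is tempered by most staff and patients being unaware of the trial, that no section reports any effect of pharmacist contact on AMA departure, and that every bias figure rests on assumed rates.

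All of this stands, and it limits the point to a conflict that arises if the criterion is applied after randomization. It does not remove the conflict. The criterion carries no time limit, foreseeable departures are already covered by its first half, and no sentence says that the ITT definition prevails. The harmonizing reading is sensible, but the reader has to supply it.

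**Conclusion.** The point holds in conditional form. As written, the AMA criterion reaches an event that, for a randomized patient, can only follow randomization. Applied to that patient it is a post-randomization exclusion that the ITT definition does not allow. This conclusion rests on the text alone and needs no assumed rate.

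The size of any harm cannot be fixed from the documents, which give no AMA frequency, no utilization rate among such patients and no difference by arm. The tabulated shifts of 0.13 to 0.47 points illustrate unequal removal; they are not estimates, and their sign depends on which arm loses more patients. Precision is barely affected. The wording should be corrected because it leaves membership of the primary analysis set open to a post-randomization event, not because a large distortion has been shown.

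**What to change.** 1. Reword the line in 5.2 along these lines: *expected to leave, or has already left, against medical advice at the time of randomization*. This keeps the legitimate screen for patients who leave before the eligibility check.
2. State in 8.3 that randomized patients who later leave AMA stay in the ITT primary analysis in the arm to which they were randomized.
3. Report the number leaving AMA after randomization, by arm, in the CONSORT diagram.
4. Leave the per-protocol set defined by receipt of the intervention, as in 8.3. AMA departure alone should not be a further reason for removal from it.
5. If any randomized patient has already been removed on this ground, restore that patient to the ITT set and record the correction.

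The cost is a few sentences. Outcomes for these patients come from the same hospital records and statewide sources as for everyone else (section 3 and Appendix A). Appendix A already requests discharge location; if that field does not identify AMA departure, one more item is needed for the counts.
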